Patients will be eligible for the study if they: 1) have been diagnosed with a new episode of depression in primary care at any of three VA study sites or associated CBOCs; 2) have a current PHQ-9 score ≥ 10 ; 3) are not receiving mental health care outside of VHA; 4) have broadband internet access at home or confirm

E.2 Study Sites and Patient Population

We have chosen our study sites, Ann Arbor, Battle Creek, Detroit), to ensure adequate numbers for the study (estimated at 330 patients, see below), patient diversity and inclusion of rural and urban areas.

All study VA medical centers have a full range of services, including primary care clinics and comprehensive (inpatient and outpatient) mental health services. These three medical centers also have a total of 9 associated Community Based Outpatient Clinics (CBOCs). The John D. Dingell VA

willingness, ability, and a plan to go to their VA or library to complete cCBT modules; 5) have familiarity with email and internet use (see below); and 6) have stable access to and ability to communicate by telephone.

[figure not shown]
We will assess patients' familiarity and self assessed comfort with the internet with questions such as "How frequently do you use the internet?" and "How often do you email?". Our threshold for being computer familiar will be relatively low, requiring only that individuals have an existing email account that they access at least once per week. In our pilot work, we found patients who met these criteria had a higher likelihood of completing the cCBT modules.

We will **include patients who have suicidal ideation** that is not immediately threatening. Suicidal ideation is common among patients in treatment for depression. Approximately 30-50% of patients in depression treatment endorse some level of suicidal ideation, although only 2-3% are a current suicide risk.(56) Peer specialists will follow the protocol used within their facility mental health services when patients confide suicidal thoughts. These protocols are clearly outlined for all staff at each of these facilities, and will be reviewed with study peer specialists during their training. The protocol for research staff when patients divulge suicidal thoughts upon screening is outlined below.

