Patients who are interested in the study will be screened for current severity of depression symptoms using the nine-item Patient Health Questionnaire (PHQ-9). The PHQ-9 has high levels of sensitivity and specificity for major depressive disorder, can be used over the telephone, and quantifies depression severity.(59)(60) Patients with PHQ-9 scores ≥ 10 , who are not receiving mental health services outside of the VA and who have broadband internet access will be eligible for the study.

Patients who endorse suicidal ideation on the PHQ-9 will be asked additional questions from a structured screener assessing suicidal history and current intent or plan. For patients who meet predetermined criteria on this screener, appropriate action plans are specified. (See suicide screener and action plans in Appendix A.) A similar telephone screener has been in place and successfully used in team members’ prior RCTs. When staff who are screening identify patients deemed at higher risk for suicide, study clinicians or the patient’s personal clinicians have been able to contact the patients in a timely manner for further evaluation and assistance.

Patients who remain eligible after telephone screening will be invited to an in-person interview at their local VA facility or CBOC. At this appointment, potential enrollees will learn more about the study and complete the informed consent process. Those patients agreeing to study participation and providing written informed consent will be randomized to either PS-cCBT or EUC. Patients will also complete their baseline assessments at this time, using Qualtrics, to familiarize them with use of this online data collection platform as their follow up-assessments will be conducted using this platform. (See section G.3.)

If the patient is randomized to PS-cCBT, the peer specialist will attend part of this interview to be introduced. If this is not logistically possible, research staff will introduce the peer specialist via video-conference on a secure internet connection.

Based on our work in the DIAL-UP reciprocal peer support study, we expect to be able to recruit approximately 1-2 patients at each site per week (3-6 per week total) for the PS-cCBT study.

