The PS-cCBT intervention and enhanced usual care (EUC) will be delivered over 12 weeks. The Beating The Blues (BTB) program consists of 8 interactive modules and recommends completing one module per week. However, we will provide 12 weeks of peer specialist support for completion of these 8 modules. Table 3 lists the components that will be delivered in each of the study treatment arms.

Table 3: Components of Treatment Arms

Enhanced Usual Care	PS-cCBT Intervention

 • Usual depression care • Patient education regarding treatment options, including antidepressants and evidence-based psychotherapies • Bi-weekly mailings with depression self management tips and local resources • Notification to the primary care clinician at 12 and 24 weeks if patient shows significant clinical worsening 	
 • Usual depression care • Access to cCBT program—Beating the Blues • Veteran peer specialist assigned • Peer specialist contacts at least once per week for 12 weeks (in-person or by telephone) to provide support and encourage cCBT participation and completion • Notification to the primary care clinician at 12 and 24 weeks if patient shows significant clinical worsening

E. 6.a Enhanced Usual Care:

As outlined above, in 2010, primary care patients newly diagnosed with depression in the study primary care settings (AA, DET, and BC and associated CBOCs) received the following treatments. Approximately 70% received an antidepressant fill, and 51% of these patients (36% overall) had an adequate trial of antidepressant (84 or days supply of antidepressant in the 114 days after first AD fill). Approximately 22% of patients had one psychotherapy visit within 14 weeks of their depression diagnosis and 3% had 8 or more psychotherapy visits within the 14 weeks following their depression diagnosis.

We assume that usual care delivered to our EUC patients will be similar to that outlined above, although our enhancements to usual care may increase treatment use slightly. (We provide these enhancements to increase the credibility and acceptability of usual care for patients randomized to this arm, please see Section E.7.)

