Threats to safety of patients in this study may also arise from the study interventions. Specifically, patients in the PS-cCBT arm may become more distressed or symptomatic through working with the cCBT modules or through their interactions with peer specialists. To mitigate this possibility, all peer specialists will be supervised by clinicians who are part of the PC-MHI team, who in turn, will work in concert with Drs. [name] and [name] who will oversee peer specialists' training and activity across study sites.

Patients' clinical status will also be systematically followed in the BTB program through the use of standardized scales (an inherent part of this clinical intervention) so that clinical worsening will be readily identified. This level of symptom monitoring is as intensive as that provided in proactive care management. If patients' symptoms are increasing significantly over time (i.e. depression scores increase >25% from baseline at more than one follow up clinical assessment point), then the supervising clinician will contact the patient and discuss their treatment progress, treatment preferences, and options for increasing the intensity of treatment.

Also, at the end of PS-cCBT participation, patients who continue with problematic symptoms will be encouraged to progress on to more intensive treatments. Please note that, PS-cCBT is not designed to “replace” more intensive and proven interventions, such as face-to-face individual CBT, but to serve as a first intervention that may provide sufficient benefit but could also serve as a “stepping-stone” to more intensive care if needed.

Potentially, patients in the study may develop suicidal ideation. Again, this will be monitored as part of the cCBT program as often as in proactive care management. The cCBT program will include information about local emergency resources as well as the Veterans Crisis Line which can provide immediate assistance. Research staff will also be available in a timely fashion and will further assess the seriousness of any emerging suicidal ideation or behaviors within 48 hours. Patients’ clinicians will also be informed and asked to follow up.

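### The 25% worsening trigger in E.8.a cannot fire from PHQ-9 baselines of 22–27 and barely can at 20–21; the gap is small and one sentence closes it

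*Combined protocol and SAP*

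**What the plan says.** E.8.a explains that the scales built into the cCBT program will be used to pick up deterioration. It defines a significant increase in symptoms, introduced by i.e., as "depression scores increase >25% from baseline at more than one follow up clinical assessment point". When that is met, "then the supervising clinician will contact the patient and discuss their treatment progress, treatment preferences, and options for increasing the intensity of treatment". The action is a conversation, not an automatic step-up, and it applies only to the PS-cCBT arm, because only that arm uses the program.

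E.8.a does not name the scale. E.6.b (Other BTB Functions) says the PHQ-9 and GAD-7 will likely be placed in every other module. E.3 requires that patients "have a current PHQ-9 score ≥ 10". Neither the inclusion nor the exclusion list caps severity.

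E.8.a also does not say which score is the baseline. The E.10 schedule lists the PHQ-9 at screening only. E.5 uses a PHQ-9 taken with the baseline measures. E.6.b would produce a first in-program PHQ-9.

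Other provisions bear on the same patients. In Table 3, both arms have "Notification to the primary care clinician at 12 and 24 weeks if patient shows significant clinical worsening", with worsening left undefined. E.8.a adds that at the end of PS-cCBT "patients who continue with problematic symptoms will be encouraged to progress on to more intensive treatments", and that research staff "will further assess the seriousness of any emerging suicidal ideation or behaviors within 48 hours".

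**The concern.** E.8.a names non-response and deterioration among the main risks to patients, and it says the modules or the peer contacts could themselves add to distress. The 25% rule is the only score criterion for depression worsening in the supplied text. Because it is relative to the patient's own baseline, the rise it demands grows with severity while the room left on the scale shrinks. At the top of the scale the demand exceeds the room.

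The rule therefore treats equal deterioration unequally. A patient who goes from 10 to 13 at two follow-ups prompts contact. A patient who goes from 22 to 25 at two follow-ups does not, although that patient is far more severely ill. At stake is a safety prompt for the most severe eligible patients in one arm.

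**Working it through.** **Inputs.** The trigger is a strict increase of more than 25% over baseline (E.8.a). The PHQ-9 has nine items (E.4). The documents do not state its item scoring; I assume 0–3 per item, so the maximum is 9 × 3 = 27. The eligible baseline is 10 or more (E.3). The IDS-SR range of 0–84 (E.9.a) serves as a check on another scale.

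**General bound.** The trigger needs a score above 1.25 × baseline, and no score can exceed the maximum M. It is impossible when 1.25 × baseline ≥ M, that is, when baseline ≥ 0.80 × M.

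**PHQ-9, M = 27.** 0.80 × 27 = 21.6, so integer baselines of 22 to 27 can never meet the rule.

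| Baseline | 1.25 × baseline | Lowest qualifying score | Rise needed | Points left |
|---|---|---|---|---|
| 10 | 12.5 | 13 | 3 | 17 |
| 15 | 18.75 | 19 | 4 | 12 |
| 20 | 25 | 26 | 6 | 7 |
| 21 | 26.25 | 27 | 6 | 6 |
| 22 | 27.5 | 28 (none exists) | 6 | 5 |
| 27 | 33.75 | 34 (none exists) | 7 | 0 |

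Baselines of 20 and 21 are possible but nearly closed. A move from 20 to 25 at two follow-ups fails, because 25 is not above 25. A move from 21 to 26 fails, because 26 is not above 26.25. Each is a 5-point rise.

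**Other readings.** Reading the rule as 25% or more leaves the same impossible set, 22–27. Reading it as 25% of the scale range (0.25 × 27 = 6.75 points) makes 21–27 impossible, but the wording ties the percentage to baseline. On the IDS-SR, 0.80 × 84 = 67.2. A baseline of 67 needs more than 83.75, so 84 qualifies; a baseline of 68 needs more than 85, which does not exist. The impossible set there is 68–84.

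**How much worsening could be missed.** From 25, 26 and 27 at most 2, 1 and 0 further points can register. E.4 shows that the PHQ-9 has a suicidal-ideation item: "Patients who endorse suicidal ideation on the PHQ-9 will be asked additional questions from a structured screener". Taking that as one item, the other eight sum to at most 8 × 3 = 24, so any score of 25 or more includes some ideation. With the ideation item fixed at s, the largest possible rise is 24 + s − baseline:

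- With s = 0: 2 points from 22, 1 from 23, 0 from 24.
- From 22 with s = 1, 2 or 3: 3, 4 or 5 points.

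The example of 22 to 25 is therefore possible with ideation unchanged at 1. The range where a sustained rise could matter and not trigger is about 20–24.

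**Which baseline.** A patient scoring 20 at screening and 22 in the first module could trigger with 26 twice on the first score, and could never trigger on the second.

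**The case against.** The strongest reply is that the trigger is one route among many, and that the clinician it would alert already sees these patients.

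- Table 3 sets peer contacts at weekly or more often for 12 weeks. E.6.b has every peer note countersigned by the supervising clinician, and peers discuss their contacts with the PC-MHI supervisor.
- E.6.b says the in-program questionnaires let overseeing clinicians reach people who are not responding. A patient going from 22 to 25 is plainly one.
- E.6.b describes a suicidality query rated 0–8 with a notification level that staff can set. It is not confined to new ideation, so it helps where the 48-hour step, worded for emerging ideation, is less clear. That matters because ideation at entry is allowed and expected: "Approximately 30-50% of patients in depression treatment endorse some level of suicidal ideation".
- Screening includes a structured suicide screener with action plans, immediate risk is excluded, and usual care continues throughout.

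Most of this stands, and it is why the gap is small. A reader might infer from the arithmetic that severe patients go unmonitored or that their decline would pass unnoticed. The documents do not support that. Nor is all of 22–27 a range of missed harm: at 27 no further worsening can register, and at 25–26 almost none can.

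What does not stand is that these routes repair the rule. None sets a score criterion for depression worsening. The Table 3 notice and the end-of-program encouragement come at or after 12 weeks, and contact of non-responders has no threshold. It is also fair that the PHQ-9 is only the likely choice, but the 80% bound applies to any scale starting at zero.

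**Conclusion.** The point holds as a minor safety-rule correction. The only stated score criterion for depression worsening in the PS-cCBT arm cannot be met from baselines at or above 80% of the scale maximum (PHQ-9 22–27), and it is nearly unreachable at 20–21. In practice the gap concerns mainly baselines of about 20–24.

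This rests on the PHQ-9 being the embedded scale and on items scored 0–3. The number of patients affected cannot be computed, because the documents give no PHQ-9 distribution. The Human Participants section, Appendix A and the PS-cCBT manual are not in the supplied text and may say more.

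A reader might also infer a threat to the trial's result. There is none: the rule prompts a clinical conversation in one arm and does not enter the 24-week comparison.

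**What to change.** Keep the 25% rule in E.8.a and add: *or, if baseline PHQ-9 is 20 or higher, any score above baseline (or remaining at 27) at more than one follow-up clinical assessment*. State which single PHQ-9 is the baseline, either the enrolment score or the first in-program score. If another scale is embedded, set the cut-off just below 80% of its maximum.

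Two simpler repairs work less well. A flat trigger at any score of 22 or more would flag improvement, such as 27 to 22; over baselines 22–27 there are 0 + 1 + 2 + 3 + 4 + 5 = 15 such improving pairs. A clause for scores at or above baseline, starting from 22, would flag 22 staying at 22 while still missing 20 to 25 and 21 to 26. The proposed clause flags sustained rises, flags stability only at the ceiling, and catches both of those cases.

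The cost is one or two sentences, with no new visits, staff or measures. The downside is a few extra supervising-clinician contacts for small rises in severe patients. It also leaves a step in the rule: a baseline of 19 still needs 24 (1.25 × 19 = 23.75), while a baseline of 20 needs only 21. For a prompt that leads to a conversation, that is acceptable.

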Primary Care Provider Mental Health Activity: Primary care clinicians may differ in their interest in and their level of activity in treating depression among their patients. Patients who are treated by primary care clinicians who actively diagnose and treat depression might receive more active depression management (more monitoring, referrals, and more medication starts and changes) than patients who are treated with clinicians who are less active in depression care. Therefore, we will construct a measure of primary care clinician depression care activity and include this measure as a covariate in study analyses. Using provider code, we will determine primary care provider antidepressant prescribing patterns (calculated as the number of antidepressant fills written by PC clinician divided by the number of patients seen by the clinician in the prior FY). We will also construct a variable for PC clinician diagnostic patterns (calculated as the number of patients who have a psychiatric diagnosis noted in an encounter by the clinician divided by the number of patients seen by the clinician in the prior FY).

Receipt of Other Health Services: We will also use VA administrative data to assess the numbers of VA primary care outpatient visits, VA specialty medical or surgical visits, emergency department visits, VA medical or surgical hospitalizations, and VA psychiatric hospitalizations. Our team has had considerable experience using administrative data to assess all of these types of health services use, and careful description of all care received is necessary when an intervention is added to usual care and a EUC control is used.(64)

Out of VA health care use will be assessed with the Cornell Service Index (CSI). The CSI was developed to assess the frequency and duration of use of a range of health services over the past three months. (85)The CSI has good inter-rater reliability with ICC for the global indices ranging between 0.97 to 1.0. Test-retest data generated Pearson correlation coefficients of 0.93 for psychiatric outpatient care and 0.83 for all visits combined.(85)

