Psychiatric and Substance Use Comorbidities. Psychiatric comorbidities may have implications for the success of the PS-cCBT intervention. We will include dichotomous indicators for the presence/absence of PTSD, another comorbid anxiety disorder, Bipolar II, or a comorbid personality disorders in study analyses. These comorbidities will be ascertained from medical records for the 12 months prior to enrollment. Although patients with severe substance use disorder will not be included in the study, we will assess potential hazardous alcohol use and non-dependent substance use.

General Medical Burden will be measured using a modified version of the Charlson Co-morbidity Index, constructed from medical record review.

The Interpersonal Support Evaluation List (ISEL)-12 is a shorter 12 item version of the ISEL, including the subscales of “appraisal”, “belonging”, and “tangible” support. Each item is rated on a four point Likert-type scale in which the subject indicates whether statements about social activities are definitely true, probably true, probably false, or probably true. The “tangible” subscale assesses the perceived availability of material aid; the “appraisal” subscale examines emotional support; and “belonging” subscale assess opportunities for shared activities. Various versions of the ISEL have demonstrated excellent reliability, validity, and internal consistency in both general and psychiatric populations. (86)

Distance to the VA service site: Distance/travel barriers may make affect the uptake and use of formal mental health services for depression. (87) We will assess the number of miles from a patient's residence to their nearest VA source of care.

Computer Literacy: Computer literacy may serve as a barrier to use of a computerized CBT program; therefore, a study-specific, 8-item measure of computer literacy will be collected to assess participants' comfort level with using a computer and internet applications, as well as how frequently they use these tools.

E.10 Schedule and Content of Study Assessments

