E.11.a Analyses of Success of Randomization: We will first determine the success of the randomization process for potential prognostic factors that may affect the primary outcomes of severity of depressive symptoms and functional status, but were not considered in minimization scheme. These factors include variables such as prior hospitalization or baseline severity of anxiety symptoms. Potential differences between groups will be determined through the use of t-tests or chi-square analyses, as appropriate. When there are significant differences in the distribution of these variables, they will be included as covariates in multivariable analyses. The interpretations of final results will also be made carefully in the presence of significant baseline differences.

E.11.b Analyses Relevant to Primary Aims: Primary study analyses will determine the effectiveness of the PS-cCBT intervention in decreasing depressive symptoms (IDS-SR), improving functioning and quality of life (VR-12, Q-LESQ-SF), and increasing recovery focus (RAS) at 24 weeks post-enrollment. We will also examine the impact of the intervention on depression coping efficacy and skills, antidepressant adherence, and initiation and completion of traditional in-person psychotherapy (contingent on symptoms).

Analyses will be of two broad types, those that assess intervention effects at each assessment point (12 weeks and 24 weeks), and those that determine effects over time. Primary analysis will be based on “intent to treat” principle, with all randomized patients included in the originally randomized group, regardless of whether they have subsequently dropped from their assigned treatment group.

Univariate Analyses: In the first phase of analysis (data verification), we will examine the distribution of all study variables to assess extreme values, missing data, variances, possible coding errors, skewness and whether or how to categorize skewed data. We will then describe means ($\pm SD$) for the continuous IDS-SR, VR-12, Q-LESQ-SF, and RAS measures by study group for each assessment time for the entire sample and

for each of the study sites, separately.

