Bivariate/Multivariate Analyses: We will evaluate bivariate associations between patients' treatment condition (PS-cCBT versus EUC) and the study outcomes to determine unadjusted measures of effect. We will also examine bivariate relationships between each of the potential covariates and the outcomes, and between each of the potential covariates and intervention group to assess possible confounders. Bivariate relationships between potential covariates will also be assessed for any collinearity in subsequent analyses.

Independent (Predictor) Variables	Dependent (Outcome) Variables
Treatment Group PS-cCBT vs Usual Care Potential Covariates Demographics Baseline measures of outcome variables Psychiatric comorbidities Study Site Social Support Prior to Enrollment General Primary Care Clinician Level of Depression Treatment Activity Distance to nearest VA facility	Primary Outcome Variables IDS-SR VR-12 Q-LES-Q-SF RAS Secondary Outcomes * Depression Coping skills (DCSES, CBTSQ) Antidepressant adherence Traditional psychotherapy use (contingent on symptoms) Hope Patient activation Anxiety Suicidal Ideation

* please note some secondary outcomes may be considered mediators in other study analyses

Effects At Each Assessment Time: Comparison at 24 weeks post-enrollment will be our primary comparison, but we will also assess patient outcomes to acute effects of the PS-cCBT intervention at 12 weeks. We will first obtain unadjusted differences in the outcomes between the two study groups with its associated 95% confidence interval. Comparisons of primary outcomes (IDS-SR, VR-12, Q-LES-Q-SF, RAS) between treatment groups at each assessment time will be accomplished using multiple regression models. Multiple regression models for each outcome variables will include the baseline values of the outcome variable as covariates to adjust for baseline differences, making the model analogous to analysis of covariance. We will also include two dummy variables for three sites and adjust for additional baseline covariates that show baseline imbalances in bivariate analyses.

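### Covariates that E.9.d includes without condition enter the E.11 model only on baseline imbalance, so the adjusted 24-week primary model is not uniquely specified

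*Combined protocol and SAP*

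**What the plan says.** Two parts of the combined protocol and SAP deal with the same baseline variables.

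**E.9.d, Other Covariates.** After explaining why clinicians may differ in how actively they treat depression, the section commits: "Therefore, we will construct a measure of primary care clinician depression care activity and include this measure as a covariate in study analyses". It defines a ratio of antidepressant fills to patients seen, and then adds: "We will also construct a variable for PC clinician diagnostic patterns". For comorbidities it says: "We will include dichotomous indicators for the presence/absence of PTSD, another comorbid anxiety disorder, Bipolar II, or a comorbid personality disorders in study analyses". None of these sentences carries a condition.

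**E.11, Study Analyses.** For prognostic factors outside the minimization scheme, E.11.a says: "When there are significant differences in the distribution of these variables, they will be included as covariates in multivariable analyses". For the primary outcomes at each assessment time, E.11.b says: "Multiple regression models for each outcome variables will include the baseline values of the outcome variable as covariates to adjust for baseline differences". It continues: "We will also include two dummy variables for three sites and adjust for additional baseline covariates that show baseline imbalances in bivariate analyses". The E.11.b variable table lists psychiatric comorbidities and clinician activity under a heading of potential covariates.

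E.12 gives a further way in: covariates found to be related to missingness are added to the models already described. E.11.b makes 24 weeks the primary comparison.

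**The concern.** E.9.d treats the clinician-activity measure and the four comorbidity indicators as settled covariates. E.11.a and E.11.b make their entry depend on a look at baseline balance, and E.12 makes it depend on a look at missingness. The document does not rank these rules. Two analysts who each follow it could fit different 24-week regressions and report different estimates, standard errors and p-values for the primary outcomes, and nothing forces the choice to be made before outcomes are seen by arm.

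The E.11 rules are also weak on their own terms. An imbalance test selects covariates by chance differences between arms and not by how strongly they predict outcome, which is what makes adjustment useful. If E.11.b governs, the adjustment that E.9.d justifies clinically will usually not be made.

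**Working it through.** **1. The plan's own figure (E.13).** Inputs: 0.4 SD, two-sided alpha 0.05, 90% power, 20% dropout.
- n per arm = 2 × (1.960 + 1.282)² / 0.4² = 131.3, rounded up to 132.
- 132 / 0.80 = 165 per arm, 330 in total. This matches E.13 exactly. No covariate enters the calculation, so the sample size does not depend on how the conflict is resolved.

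**2. The rules side by side.**

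| Term | E.9.d | E.11.b model |
|---|---|---|
| Baseline outcome | not addressed | fixed |
| Site (two dummies) | not addressed | fixed |
| Clinician-activity measure | included | only if imbalanced |
| PTSD, other anxiety disorder, Bipolar II, personality disorder | included | only if imbalanced |

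E.12 may add any of the conditional terms through missingness. The table heading in E.11.b cannot settle the matter: it also covers baseline outcome and study site, which the text of E.11.b fixes.

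**3. Number of terms.** E.9.d commits to one activity measure and says only that a second, diagnostic-pattern variable will be constructed. E.11.e describes the activity measure by the antidepressant-fill ratio. One measure plus four indicators gives five terms.

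**4. How often E.11.b would admit them.** Assumptions: tests at 5% (E.11.a says only that differences be significant, and E.11.b gives no threshold), independent, with no true difference between arms.
- None of five enters: 0.95⁵ = 0.774.
- At least one enters: 1 − 0.774 = 0.226.
- All five enter: 0.05⁵ = 3.1 × 10⁻⁷.

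Apart from the E.12 route, the full E.9.d set and the E.11.b set would therefore almost never coincide.

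**5. What the choice is worth.** Let ρ be the share of residual outcome variance explained by the five terms. The documents give no value; I assume 0.03 to 0.15.
- Standard error ratio = √(1 − ρ): 0.985 at ρ = 0.03 and 0.922 at ρ = 0.15, a reduction of 1.5% to 7.8%.
- Power at 132 per arm is 90.1% without the terms, and 90.7%, 91.5% or 92.9% if they explain 2%, 5% or 10%.
- For testing, take two z-statistics, with and without all five terms, correlated at √(1 − ρ) (2 million draws). The chance under the null that at least one exceeds 1.96 in absolute value is 5.8%, 6.0%, 6.5% and 6.8% for ρ = 0.03, 0.05, 0.10 and 0.15.
- At the planned effect, z = 0.4 / √(2/132) = 3.25. The two models then disagree on significance in 2.4% to 5.6% of trials. With a true z of 2, near the boundary, they disagree in 5.6% to 13.7%.

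**6. Cost in degrees of freedom.** With 2 × 132 = 264 completers, a model with intercept, treatment, baseline outcome and two site terms leaves 264 − 5 = 259. Five more terms leave 254.

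**The case against.** The best defence is that E.9.d is a measures section. It speaks of study analyses in general, names neither the primary model nor the 24-week regression, and writes no model. E.11.b is the later and more specific text, so a reader may let it govern and take E.9.d as the list of candidates. The comorbidities are also introduced as bearing on the success of the intervention, which suggests effect modification, and E.11.e does use clinician activity as a moderator.

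Part of this stands. A reader might infer that the document writes out two rival primary models. It does not: only E.11.b specifies a regression, and that E.9.d reaches it is an inference. The inference is reasonable, because E.11 is itself titled Study Analyses and exempts nothing. E.9.d also sits under a heading of covariates and says "include this measure as a covariate in study analyses" of clinician activity, and E.11.e does not name the comorbidities. If E.11.b were meant to govern, the E.9.d commitments would usually go unmet and would still need correcting.

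A reader might also go further than the text in three other ways:
- **Six committed terms.** E.9.d attaches its commitment to a single activity measure, so five is the natural count.
- **Adjustment is almost never made.** That is true only of all five entering together; at least one would enter in about 23% of trials, and E.12 is another route.
- **The plan has 5.8% to 6.8% type I error.** That needs an analyst who fits both models and reports the favourable one. The plan leaves room for this but does not propose it.

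**Conclusion.** The point holds as a failure to reconcile E.9.d with E.11.a, E.11.b and E.12. The covariate set of the adjusted 24-week primary model is not uniquely specified and depends on the data. That conclusion rests on the text alone.

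The size is modest and rests on assumptions. The 77% figure needs independent imbalance tests at 5%. The precision and error-rate ranges need the assumed 3% to 15% of residual variance, and compare a model with all five terms against one with none, so they are upper ends where E.11.b admits some of them. The planned-effect disagreement rate of 2.4% to 5.6% is a fairer guide than the rate near the significance boundary. Neither the validity of the randomized comparison nor the sample size of 330 is in question. The change should be made because it removes an avoidable choice at almost no cost.

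**What to change.** In E.11.b, name one primary 24-week model with a fixed covariate list, whatever the baseline balance: treatment, baseline value of the outcome, two site dummies, one defined clinician-activity measure, and the four comorbidity indicators. State which ratio is the activity measure. Take these terms out from under the potential-covariates heading in the E.11.b table, and have E.9.d refer to the list.

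Move adjustment triggered by imbalance tests (E.11.a, E.11.b) and by missingness (E.12) to labelled sensitivity analyses. Fixing the five terms while leaving those clauses in the primary model would not be enough, since the model would still depend on the data. Settle the list before 24-week outcomes are examined by arm.

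The cost is wording and about five degrees of freedom of roughly 260. The E.10 schedule shows that these variables are obtained at baseline by staff, with no patient burden. One trade-off is that predictors of missingness outside the list no longer enter the primary model, so the E.12 sensitivity analysis should be reported beside it.
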